6.0 Study Design and Procedures

6.1 Study Design

This crossover study has a within-subjects design. There will be three experimental conditions; one condition in which meals of lower energy density (ED) are served, one condition in which meals of baseline energy density are served, and one condition in which meals of higher energy density are served. The order of conditions across the three 5-day periods will be counterbalanced across classrooms. Children will be served the same amount (weight) of food and beverages across all three conditions. In the lower-ED condition, the amount of energy served over each day is ~225 calories less than in the baseline condition. Energy served over the day in the higher-ED condition is ~225 calories more than in the baseline condition. Daily menus in all conditions meet the minimum guidelines for energy and food groups outlined by the USDA and the Child and Adult Care Food Program (CACFP).

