4. On the final (16th) visit to the child care center, children will have their height and weight measured by a trained member of the study staff. Body weight will be measured in triplicate using a portable digital scale, and height will be measured in triplicate using a portable stadiometer. The children will also complete the Tasting Game, in which they are asked to taste a small food sample and point to a cartoon face that represents their liking of the food on a scale of "yucky" to "yummy".
5. Parents will be asked to complete an Evening Report form, Background Questionnaire, Children's Eating Behavior Questionnaire, Caregiver's Feeding Style Questionnaire, and Child Feeding Questionnaire. The Evening Report form will be completed at the end of each study day and returned each morning to study staff. The Background Questionnaire will be completed during the first 5-day study period and returned to study staff. The Children's Eating Behavior Questionnaire, Caregiver's Feeding Style Questionnaire, and Child Feeding Questionnaire will be administered during the last 5-day study period. All questionnaires will be completed using paper copies.
6. Photographs may be taken of children eating meals, participating in the Tasting Game, or having their height and weight measured.
7. There will be a 1-week break between 5-day study periods. There will be a 4- to 6-week wash-out period between this experiment and Experiments 1 and 3 at each child care center. We will rotate the participating child care centers to ensure that each child completes the wash-out and is eligible to participate in the next experiment if they choose.
8. Approved study staff (on this application) will email parents on the Friday before a study week begins to remind parents of the upcoming study week.
9. Teachers will be asked to complete one questionnaire (Caregiver's Feeding Style Questionnaire) per participating child in their classroom. Teachers will only complete questionnaires about children who are enrolled in the study. This questionnaire will be administered using a paper copy. Teachers will be verbally informed by study staff about the children for whom they are to complete questionnaires.
10. Data from questionnaires completed by teachers will be linked to child participants by a three digit number and letter only.

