8.2 Statistical methods

The main outcomes of the study are daily consumption (by weight, ED, and energy) of manipulated foods, non-manipulated foods and milk, and their combined total. Other outcomes are cumulative intake for the entire 5 days, daily macronutrient intake, daily intake of non-manipulated items by meal component (fruits and vegetables at main meals, grain-based snacks, dairy snacks, fruit and vegetable snacks, and milk), and

physical activity time (daily step counts, sedentary time, and moderate-to-vigorous time). To analyze differences in mean daily outcomes across the 3 experimental conditions, linear mixed models with repeated measures are used. The fixed factors in the models are ED condition (lower-ED, baseline-ED, or higher-ED), study week, study day, menu, classroom, and sex. Interactions between these factors are tested and removed from the model if not significant. Participants are treated as a random effect. The Tukey-Kramer method is used to adjust for multiple pairwise comparisons between means. In order to evaluate the contribution to children's intakes of non-study foods reported by parents, the energy content of the reported items is estimated by study staff. The outcome of daily energy intake is analyzed both with and without the non-study items. This estimated data is not included in further analyses, because these estimates are based on parental recall and were less accurate than measured intake.

Random coefficients models are used to test whether the trajectories of daily intake in the 3 conditions converge over the 5 days, i.e., whether regulation of energy intake occurs over time in response to ED variations. The trajectories of intake over time are modeled separately for each child and allowed to vary randomly. Time (study day) is treated as a continuous covariate in the model and polynomial factors of time (linear and quadratic coefficients) are tested as both fixed and random effects to determine the shape of the intake trajectory. The intercept of the trajectory reflects the magnitude of daily intake. The linear coefficient represents the rate of change in intake (slope) across time after Day 1, and the quadratic coefficient represents the rate of acceleration or deceleration in intake (curvature) across time after Day 1.

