The influence of continuous participant characteristics (age, body weight, height, BMI-for-age percentile, BMI z-score, step counts, and questionnaire subscales) on the relationship between the experimental factors and intake is assessed by analysis of covariance with linear mixed models. Because multiple participant characteristics are tested as covariates, the method of Benjamini and Hochberg [6] is used to adjust the significance levels, with the false discovery rate set at 0.05 [6]. In order to standardize for energy needs, models having significant covariance with weight status are adjusted for estimated energy requirements [7]. Differences in subject characteristics between boys and girls, as well as differences in intake between children with and without obesity (sex-specific BMI-for-age percentile ≥ 85 and < 85 , respectively), are assessed by independent-samples t-tests. Within conditions, the means of daily energy intakes expressed as a percentage of estimated energy requirements are compared to 100% using a one-sample t-test and controlling the family-wise error rate using the Bonferroni correction.

It has been predetermined that children who have incomplete intake measures on ≥ 3 days in all 3 conditions will be excluded from analysis. It has also been predetermined that children who eat $> 95\%$ of the food weight served on at least 1 day will be classified as "plate cleaners", and their influence on the results will be tested. To evaluate whether the distribution of taste ratings (yummy, just okay, yucky) of the lunch and snack dishes differs significantly across experimental conditions, ordinal logistic regression is used; results are reported as odds ratios (OR) with 95% confidence intervals. Outcomes from

statistical models are reported as mean \pm SEM and subject characteristics are reported as mean \pm SD. Standardized effect sizes are calculated using Cohen's d statistic, with no adjustment for correlation due to repeated measures. Results are considered significant at $P < .05$. All data are analyzed using SAS software (SAS 9.4, SAS Institute, Inc., Cary, North Carolina, USA).

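### The taste-rating analysis specifies no handling of repeated ratings from the same child, so its odds-ratio intervals and P values may be miscalibrated, in a direction the plan does not let the reader determine

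*Combined protocol and SAP*

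**What the plan says.** Section 8.2 of the combined protocol and SAP sets out to test whether the "distribution of taste ratings (yummy, just okay, yucky) of the lunch and snack dishes differs significantly across experimental conditions". The method is one clause: "ordinal logistic regression is used; results are reported as odds ratios (OR) with 95% confidence intervals". No child effect, cluster variable, robust variance or dish term is mentioned.

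The ratings come from the Tasting Game in section 6.2, item 4. Its timing is "On the final (16th) visit to the child care center", after all three periods, and the task is described thus: "they are asked to taste a small food sample and point to a cartoon face that represents their liking of the food". The number of dishes, and which energy-density versions each child tastes, are not given.

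For intake, the same section is explicit. In the linear mixed models of daily outcomes, "Participants are treated as a random effect". The convergence analysis gives each child a random trajectory, and the covariate analyses again use linear mixed models. Nothing carries these provisions over to the taste analysis.

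**The concern.** A child who likes most foods will tend to rate most samples favourably, so ratings from one child are likely to be correlated. A cumulative-logit model with no further specification treats them as if each came from a different child. Its standard errors are then wrong unless the correlation is negligible or each child supplies only one rating.

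The practical stake is palatability. Section 6.2 says the conditions differ only in energy density. The taste comparison is the one planned statistical check that could show the versions also differed in liking, which would be a rival explanation for an intake difference. Intervals that are too narrow could suggest a liking difference that is not there; intervals that are too wide could hide a real one. The plan does not state this purpose for the taste analysis; it is inferred from the design.

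**Working it through.** **Plan's own figure.** There is none to reproduce: the documents give no odds ratio, interval, power, dish count or correlation for taste. The 45 required and 55 enrolled children in section 8.1 were derived for the intake trajectory.

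**Are there several ratings per child?** Section 8.2 speaks of dishes in the plural, covering lunch and snacks. Section 6.3 allows an extra hour for the Tasting Game together with height and weight. Section 6.2 describes the task with a single food sample but gives no count. Several ratings per child is therefore a strong inference, not a stated fact.

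**Inputs.** From the documents: three rating categories, three conditions, alpha 0.05, and 45 children (section 8.1). Assumed: 3 or 6 dishes, latent intraclass correlation (ICC) of 0 to 0.3, and the tasting design. The latent ICC is s²/(s² + π²/3), where s is the SD of the child intercept; for ICC 0.3, s² = (0.3/0.7) × 3.29 = 1.41.

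**Simulation.** True odds ratio 1, normal child intercept, proportional-odds model fitted without a child effect, 2-df Wald test of condition, 400 replicates per cell. Each entry is the type I error, then the coverage of the nominal 95% interval, then model SE divided by empirical SE.

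| Dishes | ICC | One version per child | All three versions of each dish | Versions rotated over dishes within child |
|---|---|---|---|---|
| 3 | 0 | 0.043 / 0.940 / 0.94 | 0.048 / 0.940 / 0.99 | 0.050 / 0.953 / 1.00 |
| 3 | 0.1 | 0.072 / 0.925 / 0.90 | 0.033 / 0.953 / 1.01 | 0.048 / 0.955 / 0.98 |
| 3 | 0.2 | 0.110 / 0.890 / 0.82 | 0.030 / 0.960 / 1.16 | 0.025 / 0.955 / 1.05 |
| 3 | 0.3 | 0.107 / 0.880 / 0.79 | 0.020 / 0.975 / 1.13 | 0.028 / 0.970 / 1.08 |
| 6 | 0 | 0.060 / 0.930 / 0.98 | 0.043 / 0.960 / 1.01 | 0.035 / 0.970 / 1.05 |
| 6 | 0.1 | 0.100 / 0.905 / 0.85 | 0.048 / 0.938 / 1.02 | 0.035 / 0.975 / 1.13 |
| 6 | 0.2 | 0.207 / 0.843 / 0.70 | 0.033 / 0.960 / 1.06 | 0.018 / 0.965 / 1.11 |
| 6 | 0.3 | 0.250 / 0.815 / 0.66 | 0.030 / 0.975 / 1.15 | 0.018 / 0.985 / 1.17 |

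Where all three versions are tasted, a child gives 3 × 3 = 9 or 6 × 3 = 18 ratings. Monte Carlo error is about 0.01 to 0.02 per rate; for example, √(0.25 × 0.75/400) = 0.022.

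**Hand check.** For one version per child, the SE ratio should be near 1/√[1 + (m − 1) × ICC], with m ratings per child. For m = 3, ICC 0.3: 1/√1.6 = 0.79 (simulated 0.79). For m = 6, ICC 0.3: 1/√2.5 = 0.63 (simulated 0.66).

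**Second simulation, stronger correlation.** 48 children, 3 or 6 ratings each, likelihood-ratio test, 600 replicates per cell:

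| ICC | Ratings | Version varies between children | Version varies within child |
|---|---|---|---|
| 0.23 | 3 | 0.14 | 0.028 |
| 0.23 | 6 | 0.22 | 0.022 |
| 0.41 | 3 | 0.18 | 0.022 |
| 0.41 | 6 | 0.30 | 0.015 |

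**Combined.** For ICC from 0.1 to 0.41, the nominal 5% test rejects about 7% to 30% of the time when version varies between children, and about 1.5% to 5% when it varies within child. At ICC 0 it stays near nominal (0.035 to 0.060).

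**The case against.** The best defence is that the plan is silent, not wrong. Ordinal logistic regression is a family that includes mixed and GEE forms, and analysts who give children random effects throughout the intake models may well do so here. A reader might infer that the plan fits the model with no child effect, or that its liking intervals are wrong. The documents support neither: they do not exclude a child effect, and they contain no liking interval or P value that could be wrong. This stands, and limits the point to what is left unspecified. It does not remove it: the section names its method for within-child correlation elsewhere, so a programmer following the taste sentence literally would fit the independent-ratings model.

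It can also be said that the alarming rates need each child to taste one version only, while section 6.1 states: "This crossover study has a within-subjects design". That is fair, and a reader should not take 30% as the expected false-positive rate. The crossover, however, settles which meals a child is served, not which versions appear in a single tasting session held after all three periods. Either design remains open.

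Finally, taste is not in the hypotheses, the endpoints of sections 1.2 and 1.3, or the main and other outcomes of section 8.2. This also stands. A reader might infer that the intake findings are compromised; they are not, because those models carry their own child effects.

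**Conclusion.** The point holds as a gap in specification with a concrete remedy. If the taste model is fitted as named and children give several correlated ratings, its 95% intervals and P values may be invalid. They would be too narrow if each child rates one version (type I error about 7% to 30%), and near nominal to too wide if versions vary within child (about 1.5% to 5%). The statement that the model fails under every tasting design goes too far: within-child designs were near nominal at ICC 0.1, and one rating per child or an ICC near 0 leaves no material error.

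The figures rest on assumed ICCs, dish counts and tasting designs, none of which is in the documents. Only null rejection rates were computed; a conservative test implies lost power, but the loss was not quantified. The consequence is confined to a supporting analysis of liking.

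**What to change.** In section 8.2, specify a cumulative-logit mixed model with a random child intercept and dish as a fixed factor, or alternatively GEE or cluster-robust standard errors with child as the cluster. Report the condition odds ratios and 95% intervals from that model. Say which form is used, because the mixed-model odds ratio is child-specific and the GEE one is population-averaged.

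In section 6.2, item 4, state how many dishes and how many versions of each dish every child rates. That tells the reader whether the condition contrast lies within or between children.

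The cost is a sentence or two in the plan and minor extra modelling work. No new data are needed, and the mixed model can be fitted in SAS 9.4, which the plan already names.

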9.0 Confidentiality, Privacy and Data Management

9.1 Confidentiality

We may take photographs of children eating meals, participating in the Tasting Game, or having their height and weight measured, which may be used for poster or oral presentations at scientific meetings. Parents will indicate on their consent form if they agree to have their child's photograph taken. All images will be stored on a password-protected network drive which can be accessed only by those identified on this application. Images will be stored with a generic title and will not be labeled with any identifiable information. The images will be deleted from the network drive within 3 years of completion of the study.

9.1.1 Identifiers associated with data and/or specimens

Children's data will only be identified by a 3 digit number, dot color, and a letter of the alphabet. Teachers will not have their own identifiers.

9.1.1.1 Use of Codes, Master List

The list that links the ID code to subject identifiers will be stored in a locked closet in the Lab Manager's office in [name]. Only those listed on this application will have access to it. The master list of the codes will be destroyed upon publication of the study or five years after the close of the study, whichever comes first.

9.1.2 Storage of Data and/or Specimens

Paper data with identifiers will be stored in a locked cabinet in a locked closet in the Lab Manager's office. Data on network drives will have no identifiable information. Access to network drives is protected by passwords.

Paper and digital copies of data with identifiers removed will be stored indefinitely. This study will be issued a Certificate of Confidentiality. Researchers will not disclose or provide any identifiable information without the subject's prior consent or where permitted according to NIH's Policy on Issuing Certificates of Confidentiality.

9.1.3 Access to Data and/or Specimens

Only those listed on this application will have access to data.

9.1.4 Transferring Data and/or Specimens

The researchers do not plan to release identifiable information collected in the study. However, if researchers consider releasing identifiable information in the future – the individual or institution receiving the identifiable information will be made aware they are also subject to the requirements of subsection 301(d) of the Public Health Service Act.

9.2 Privacy

No personal information other than first name, telephone number, and email address is stored where it can be seen by study staff. Participant data will remain unidentified except by study number and letter. Only senior staff members listed on this application have access to personal information such as address, age, weight, etc.

Data on food consumption is collected in a separate room where only study staff is present. Heights and weights for both children and parents are collected in a private area of the child's classroom.

10.0 Data and Safety Monitoring Plan

The proposed study poses minimal risk to participants, since the procedures involve little change from the usual meals and activities at the child care centers.

11.0 Risks

There are minimal risks associated with participation in this project. The risks are no greater than those associated with the children's usual attendance and consumption of meals at the child care center and at home, which include the risk of food allergy, food-borne illness, and choking on food.

The amounts served in all conditions meet or exceed minimum requirements for calorie and nutrient content for this age group as specified by the UDSA and the Child and Adult Care Food Program (CACFP).

There are no potential risks for teacher participants.

12.0 Potential Benefits to Subjects and Others

12.1 Potential Benefits to Subjects

There are no direct initial benefits to subjects participating in the proposed study.

12.2 Potential Benefits to Others

The research will benefit society by advancing understanding of children's eating behavior and identifying meal-related strategies for the prevention of obesity in children.

13.0 Sharing Results with Subjects

No results will be shared with the subjects.

14.0 Economic Burden to Subjects

14.1 Costs

N/A

14.2 Compensation for research-related injury

It is the policy of the institution to provide neither financial compensation nor free medical treatment for research-related injury. In the event of injury resulting from this research, medical treatment is available but will be provided at the usual charge. Costs for the treatment of research-related injuries will be charged to subjects or their insurance carriers.

16.0 Adverse Event Reporting

16.1 Reporting Adverse Reactions and Unanticipated Problems to the Responsible IRB

In accordance with applicable policies of The Pennsylvania State University Institutional Review Board (IRB), the investigator will report, to the IRB, any observed or reported harm (adverse event) experienced by a subject or other individual, which in the opinion of the investigator is determined to be (1) unexpected; and (2) probably related to the research procedures. Harms (adverse events) will be reported to the IRB in accordance with the IRB policies and procedures.

16.2 Auditing and Inspecting

The investigator will permit study-related monitoring, audits, and inspections by the Penn State quality assurance program office(s), IRB, the sponsor, and government regulatory bodies, of all study related documents (e.g. source documents, regulatory documents, data collection instruments, study data etc.). The investigator will ensure the capability for inspections of applicable study-related facilities (e.g. pharmacy, diagnostic laboratory, etc.).

17.0 Study Monitoring, Auditing and Inspecting

17.1 Auditing and Inspecting

The investigator will permit study-related monitoring, audits, and inspections by the Penn State quality assurance program office(s), IRB, the sponsor, and government regulatory bodies, of all study related documents (e.g. source documents, regulatory documents, data collection instruments, study data etc.). The investigator will ensure the capability for inspections of applicable study-related facilities (e.g. pharmacy, diagnostic laboratory, etc.).

